4.2.2.1 Everolimus and drugs influencing CYP3A4 enzyme

Everolimus is a substrate of CYP3A4, and a substrate and moderate inhibitor of the multidrug efflux pump, PgP (PgP, MDR1, and ABCB1). Therefore, extent of absorption and subsequent elimination of systemically absorbed everolimus may be influenced by products that are substrates, inhibitors, or inducers of CYP3A4 and/or PgP. Concurrent treatment with strong CYP3A4-inhibitors should be avoided. Inhibitors of PgP may decrease the efflux of everolimus from brain or tumor and therefore increase everolimus concentrations in these tissues. In vitro studies showed that everolimus is a competitive inhibitor of CYP3A4 and of CYP2D6, potentially increasing the concentrations of products eliminated by these enzymes. Thus, caution should be exercised when co-administering everolimus with CYP3A4 and CYP2D6 substrates with a narrow therapeutic index. Clinical studies have been conducted in healthy subjects to assess pharmacokinetic drug interactions between everolimus and potential CYP3A modifiers (ketoconazole, verapamil, erythromycin, rifampin, midazolam, and HMGCoA reductase inhibitors (statins)).

Table 14 Clinically relevant drug interactions: inducers, and inhibitors of isoenzyme CYP3A

Inducers

Strong inducers: avasimibe, carbamazepine, mitotane, phenobarbital, phenytoin, rifabutin, rifampin (rifampicin), St. John's wort (hypericum perforatum)
 
Moderate inducers: bosentan, efavirenz, etravirine, genistein, modafinil, nafcillin, ritonavir, [talviraline], thioridazine, tipranavir
 
Weak inducers: amprenavir, aprepitant, armodafinil (R-modafinil), bexarotene, clobazam, danshen, dexamethasone, Echinacea, garlic (allium sativum), ginkgo (ginkgo biloba), glycyrrhizin, methylprednisolone, nevirapine, oxcarbazepine, pioglitazone, prednisone, [pleconaril], primidone, raltegravir, rufinamide, sorafenib, telaprevir, terbinafine, topiramate, [troglitazone], vinblastine

Inhibitors

Strong inhibitors: boceprevir, clarithromycin, cobicistat, conivaptan, elvitegravir, indinavir, itraconazole, ketoconazole, lopinavir, mibefradil, nefazodone, nelfinavir, posaconazole[100], ritonavir, saquinavir, telaprevir, telithromycin, tipranavir, troleandomycin, voriconazole
 
Moderate inhibitors: Amprenavir, aprepitant, atazanavir, casopitant, cimetidine, ciprofloxacin, cyclosporine, darunavir, diltiazem, dronedarone, erythromycin, fluconazole, fosamprenavir, grapefruit juice (citrus paradisi fruit juice), imatinib, schisandra sphenanthera, tofisopam, verapamil

Table 15 Clinically relevant drug interactions: substrates, inducers, inhibitors of PgP and PgP/CYP3A dual inhibitors

Substrates
colchicine, digoxin, fexofenadine, indinavir, paclitaxel, talinolol, topotecan, vincristine, everolimus
Inducers
rifampin, St John's wort
PgP Inhibitors and PgP/CYP3A Dual Inhibitors
amiodarone, azithromycin, captopril, carvedilol, clarithromycin, conivaptan, diltiazem, dronedarone, elacridar, erythromycin, felodipine, fexofenadine, fluvoxamine, ginkgo (ginkgo biloba), indinavir, itraconazole, lopinavir, mibefradil, milk thistle (silybum marianum), nelfinavir, nifedipine, nitrendipine, paroxetine, quercetin, quinidine, ranolazine, rifampin, ritonavir, saquinavir, Schisandra chinensis, St John's wort (hypericum perforatum), talinolol, Telaprevir, telmisartan, ticagrelor, tipranavir, tolvaptan, valsopodar, verapamil
Reference: Internal Clinical Pharmacology Drug-drug interaction (DDI) memo, updated Oct. 2, 2011,29-Oct-2012 which summarizes DDI data from three sources including the FDA's "Guidance for Industry, Drug Interaction Studies", the University of Washington's Drug Interaction Database, and Indiana University School of Medicine's Drug Interaction Table.

4.2.3 Vaccinations

Immunosuppressants may affect the response to vaccination and vaccination during treatment with everolimus may therefore be less effective. The use of live vaccines should be avoided during treatment with everolimus. For pediatric patients with SEGA that do not require immediate treatment, complete the recommended childhood series of live virus vaccinations prior to the start of therapy according to local treatment guidelines. Examples of live vaccines are: intranasal influenza, measles, mumps, rubella, oral polio, BCG, yellow fever, varicella, and TY21a typhoid vaccines.

5 BIOSPECIMEN COLLECTION

5.1 SAMPLE COLLECTION FOR GENOTYPING AND RESEARCH STUDIES

5.1.1 Tumor Sample

Within 4 weeks prior to initiation of treatment with the respective study agent (everolimus or sunitinib), patients who meet eligibility criteria, will undergo biopsy of the primary tumor or any metastatic site for molecular analyses. Patients will undergo a percutaneous core needle (16 or 18 gauge) biopsy of the tumor under local anesthesia if there are no paraffin blocks available of tumor sample previously removed or biopsied. These percutaneous biopsies will be performed by interventional radiology (CT scan or ultrasound guidance). If needed, patients will be offered conscious sedation for the biopsy procedure. Sample collection will be performed according to standard operating procedures. Four core needle biopsies will be obtained, three samples will be formalin fixed and sent to the Laboratory of Pathology in the NCI for histological study. The official pathology report and samples will then be taken to [name] laboratory:

[name], Email: [contact]

CANCER GENETICS BRANCH

[name],

[name],

[contact]

The remaining sample will be immediately placed in cryovials, snap frozen on liquid nitrogen or dry ice and transported to [name] laboratory.

Fresh tissue samples should be collected into empty, unused cryovials (Nunc catalog #5001-0012, 5001-1020 or equivalent) on dry ice or liquid nitrogen. Samples may be obtained by FNA or core biopsy.

The interval between sample acquisition and freezing on dry ice must not exceed 30 minutes. Frozen, vialled samples should be transferred from dry ice to -80°C (minimum) or liquid nitrogen frozen storage within 2 hours.

Samples will be recorded in LabMatrix and reviewed by the Laboratory of Pathology to confirm the diagnosis. The remaining sample will be transported to [name] laboratory [[name]., [name], [name], [contact], Email: [contact]] for tumor genotyping along the saliva DNA.

5.1.2 Saliva Collection and Peripheral Blood

Saliva specimen (2-13 ml) will be obtained for targeted sequencing and comparison to tumor sequencing results and mutation calls before treatment. The saliva samples will be collected by a saliva collecting kit with complete and detailed instructions for collection available in the kit and on manufacturer's website at <http://www.dnagenotek.com/ROW/products/OG500.html> (an alternative saliva collecting kit can be used if needed). The saliva will be processed by and stored in the laboratory of [name] and will be used as an autologous control for future genomic studies.

3 mL of saliva will be collected using the Oragene saliva collection kit (DNA Genotek). The sample may be collected at any time after informed consent has been obtained, but collection is preferred at baseline.

Ideally, the patient should be advised not to eat or drink anything 30 minutes prior to collection.

Once the sample is obtained, the top of the device is closed, releasing a preservative, the top is removed, and a cap is placed on the tube.

The date and exact time of the collection should be recorded on the sample.

Samples will be recorded in LabMatrix. DNA will be extracted from the saliva samples and the DNA sample (along with the coded, linked tumor sample) will be transported to [name] laboratory. [name] will not have access to the sample code key.

Peripheral blood (30 mL) may be obtained for targeted sequencing and comparison to tumor sequencing results and mutation calls after enrollment and before treatment. The blood will be processed by and stored in the laboratory of [name] and will be used as an autologous control for future genomic studies.

Test/assay	Volume (approx.)	Type of tube	Collection point	Location of specimen analysis
Molecular Analysis	4 Core Tumor Biopsies		Screening	[name] lab
Targeted Sequencing & Autologous Control	2-13 ml Saliva	Saliva Collecting Kit	Baseline	[name] lab
Targeted Sequencing	30 ml Serum		Baseline	[name] lab

5.2 SAMPLE STORAGE, TRACKING AND DISPOSITION

5.2.1 Procedures for Storage of Specimens in the Laboratory of [name]

- In patients who undergo biopsy, the samples will be immediately snap frozen in liquid nitrogen and transported to the [name] Lab by calling [contact]. Samples will be labeled with the date and time of acquisition, the type of tissue and patient study ID. Upon receipt in the lab, samples will be bar coded and logged in to the tissue

database, LabMatrix. Samples will be stored in -20°C or -80°C freezers until molecular analysis. All freezers are monitored and are on separate emergency generator lines.

- Saliva and serum samples for correlative studies may also be obtained and will be stored and tracked in the same manner as tissue samples.
- At the completion of the protocol, the investigator will dispose of all specimens in accordance with the environmental protection laws, regulations and guidelines of the Federal Government and the State of Maryland.
- Samples at NIH will be ordered in CRIS and tracked through a Clinical Trial Data Management system. Should a CRIS screen not be available, the CRIS downtime procedures will be followed. Samples will not be sent outside NIH without IRB notification and an executed MTA.
- All specimens obtained in the protocol are used as defined in the protocol. Any specimens that are remaining at the completion of the protocol will be stored in the conditions described below. The study will remain open so long as sample or data analysis continues. Samples from consenting subjects will be stored until they are no longer of scientific value or if a subject withdraws consent for their continued use, at which time they will be destroyed. The PI will report any loss or destruction of samples to the NIH IRB as soon as he is made aware of such loss
- If the patient withdraws consent the participant's data will be excluded from future distributions, but data that have already been distributed for approved research use will not be able to be retrieved.
- The PI will report destroyed samples to the IRB if samples become unsalvageable because of environmental factors (ex. broken freezer or lack of dry ice in a shipping container) or if a patient withdraws consent. Samples will also be reported as lost if they are lost in transit between facilities or misplaced by a researcher. Freezer problems, lost samples or other problems associated with samples will also be reported to the IRB, the NCI Clinical Director, and the office of the CCR, NCI.

5.2.2 Procedures for Storage of Tissue Specimens in the Laboratory of Pathology

Tissues designated for clinical diagnostics are transported to the Laboratory of Pathology (LP) where they are examined grossly, and relevant portions are fixed, embedded in paraffin and sectioned and stained for diagnostic interpretation. Unutilized excess tissues are stored for up to three months, in accordance with College of American Pathologists/Joint Commission on Accreditation of Healthcare Organizations (CAP/JCAHO) guidelines, and then discarded. Following completion of the diagnostic workup, the slides and tissue blocks are stored indefinitely in the LP's clinical archives. All specimens are catalogued and retrieved utilizing the clinical laboratory information systems, in accordance with CAP/JCAHO regulations. The use of any stored specimens for research purposes is only allowed when the appropriate IRB approval has been obtained. In some cases, this approval has been obtained via the original protocol on which the patient was enrolled

5.3 SAMPLES FOR GENETIC/GENOMIC ANALYSIS

5.3.1 Description of the scope of genetic/genomic analysis

- Tumor genotyping: Somatic mutation analysis of tumor biopsy specimens will be performed by sequencing 197 driver genes (**Appendix C**) in a CLIA certified genetic laboratory.
- Germline sequencing for 197 driver genes (**Appendix C**) will be performed on saliva samples or peripheral blood samples in a CLIA certified genetic laboratory
- Histology: Tissues may be examined by standard histology, immunohistochemistry and or in situ hybridization in the Laboratory of Pathology, NCI.

5.3.2 Privacy and Confidentiality of medical information/biological specimens

Fresh tumor and blood samples will be stored in a minus 80-degree freezer. The samples of each patient will be assigned a study ID number, and that number will be used in all laboratory studies. At no time will patient's names be used on the blood and tissue samples. The molecular studies will be done in the CLIA certified genetic laboratory of [name]. Sometimes, because a group collaboration or journal policy requires it, a subject's genetic data may be deposited in a database such as dbGaP. Although there is controlled access to such a database, such a submission carries theoretical risks of revealing the identity of the subject. This is discussed in the consent.

5.3.3 A Certificate of Confidentiality will be obtained for the study as described in Section 10.3.1.5.

5.3.4 Management of Results

The results of molecular studies will be communicated to the patient. Other than initial determination of the presence of particular genetic alteration(s) outlined in **Appendix C** and **Appendix D**, the results of subsequent molecular studies are for research purposes only and will not be communicated to the patient. The exceptions to this are potential incidental findings that are deemed medically significant and actionable.

Subjects, treated in NCI will be contacted if a clinically actionable gene variant is discovered. Clinically actionable findings for the purpose of this study are defined as disorders appearing in the American College of Medical Genetics and Genomics recommendations for the return of incidental findings that is current at the time of primary analysis. (A list of current guidelines is maintained on the CCR intranet: <https://ccrod.cancer.gov/confluence/display/CCRCRO/Incidental+Findings+Lists>). Subjects who still remain on the study will be contacted at this time with a request to provide a blood sample to be sent to a CLIA certified laboratory.

5.3.4.1 Genetic counseling in NCI

If the research findings are verified in the CLIA certified lab, the subject will be offered the opportunity to come to NIH (at our expense) to have genetic education and counseling with the NCI Genetics Branch to explain this result. If the subject does not want to come to NIH, a referral to a local genetic healthcare provider will be provided (at their expense). This is the only time during the course of the study that incidental findings will be returned. No interrogations regarding clinically actionable findings will be made after the primary analysis

6 DATA COLLECTION AND EVALUATION

6.1 DATA COLLECTION

The PI will be responsible for overseeing entry of data into a password protected electronic system (NCI C3D) and ensuring data accuracy, consistency and timeliness. Clinical data will be entered into the NCI C3D electronic database at least once every two weeks when patients are enrolled on the trial. Protocol-specific eCRFs will be developed for this trial in C3D. The principal investigator, associate investigators/research nurses and/or a contracted data manager will assist with the data management efforts.

All data obtained during the conduct of the protocol will be kept in secure network drives or in approved alternative sites that comply with NIH security standards. Primary and final analyzed data will have identifiers so that research data can be attributed to an individual human subject participant.

The NCI investigators will be responsible for the collection, maintenance, and quality control of the study data.

Labmatrix will be used for sample data collection. Data in this system will be entered by the NCI staff.

All adverse events, including clinically significant abnormal findings on laboratory evaluations, regardless of severity, will be followed until return to baseline or stabilization of event. Patients will be followed for adverse events for at least 30 days after removal from study treatment or until off-study, whichever comes first.

An abnormal laboratory value will be recorded in the database as an AE **only** if the laboratory abnormality is characterized by any of the following:

- Results in discontinuation from the study
- Is associated with clinical signs or symptoms
- Requires treatment or any other therapeutic intervention
- Is associated with death or another serious adverse event, including hospitalization.
- Is judged by the Investigator to be of significant clinical impact
- If any abnormal laboratory result is considered clinically significant, the investigator will provide details about the action taken with respect to the test drug and about the patient's outcome.

End of study procedures: Data will be stored according to HHS, FDA regulations and NIH Intramural Records Retention Schedule as applicable.

Loss or destruction of data: Should we become aware that a major breach in our plan to protect subject confidentiality and trial data has occurred, the IRB will be notified.

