Hematologic	Continue at the same dose level.	Withhold dose until toxicity is Grade ≤ 2 or has returned to baseline, then resume treatment at the same dose level ² . If the toxicity recurs with Grade 3 severity, at the discretion of the investigator, reduce the dose by 1 level	Withhold dose until toxicity is Grade ≤ 2 or has returned to baseline, then reduce the dose by 1 level and resume treatment ²

¹If after the first 8 weeks there is no response according to RECIST and toxicity remains \leq non-hematological Grade 1 or \leq hematological Grade 2 dose escalation to 50 mg/day may be considered.

² Patients who develop grade 4 hyperuricemia or grade 3 hypophosphatemia without clinical symptoms may continue study treatment without interruption at the discretion of the investigator. Nausea, vomiting, or diarrhea must persist at grade 3 or 4 despite maximal medical therapy. Patients who develop Grade 3 or 4 lymphopenia may continue study treatment without interruption. Complicated neutropenia includes duration of Grade 4 longer than 7 days or concurrent fever or infection.

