6.1.2 Case Report Forms

Data may be entered from the source documents directly into eCRFs in C3D for each patient enrolled in this study. The principal investigator or research nurse will review the eCRFs for completeness and accuracy. Site personnel may also conduct independent audits to ensure completeness and accuracy of data in C3D.

Only the following adverse events will be recorded on the Case Report Form:

- Grade 2 unexpected events that are possibly, probably or definitely related to the study drugs;
- Grade 3 and 4 events that are possibly, probably or definitely related to the study drugs;
- Grade 5 events regardless of attribution;
- Serious Events regardless of attribution.

Patients who meet the standard of care criteria for resection of their disease will undergo a major operative procedure and may receive extensive care in the ICU. The principal investigator or designee will closely monitor and document the clinical care and treatment of each patient as per standard of care at the NIH Clinical Center. As per NIH Clinical Center standards of practice, the Occurrence Reporting System will be used to report any clinical events meeting these reporting criteria.

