80% and 95% confidence intervals to explore whether the present results exceed those from prior studies. In addition, the Kaplan-Meier curves for all patients who received either sunitinib and everolimus as their treatments may be combined into one pooled Kaplan-Meier curve if the two curves for these treatments are sufficiently similar to one another ($p > 0.30$ by a two-tailed log-rank test). This combined curve will then be evaluated relative to the published median of 11 months PFS for each arm to provide a more powerful comparison relative to the historically expected results. In addition, Kaplan-Meier curves limited to the patients who received targeted therapy based solely on mutation status may be constructed for exploratory and descriptive purposes.

Response and overall survival will also be evaluated as secondary endpoints, based on the patients treated with sunitinib or everolimus, using all patients receiving treatment. These results will be descriptive and may consist of fractions of responses as well as Kaplan-Meier curves for survival. The association between genotype and PFS will be explored by evaluating the results within a treatment based on the major genotype categories identified. Safety will be evaluated by tabulating and reporting the distribution of the worst grade of each type of toxicity found, per patient, separately by arm. Should any particular type of toxicity result in 5 or more patients with grade 3-4 toxicity, a comparison of the distributions of toxicity between the two arms may be performed using a Cochran-Armitage test for trend.

Because the patients may not end up being assigned in equal proportions to the two arms, and because the goal is to have 44 evaluable patients who have received each treatment, additional patients beyond the 44 described above may be enrolled on the arm with faster accrual. As such, the study will have an accrual ceiling of 120 patients, with accrual ending when there are 44 evaluable patients on the arm with fewer patients. An amendment may also be needed if a lower proportion of patients than expected receive study drug therapy or if a high portion of treated patients are not evaluable for response. It is anticipated that 20-30 patients per year may enroll onto this trial; thus, accrual may be completed in 4-5 years.

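### Section 6.1 decides which laboratory values become AEs without regard to CTCAE grade, so asymptomatic, untreated Grade 3-4 laboratory toxicities can be missing from the Section 8 toxicity table; the Section 8 trigger also leaves out grade 5

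*Combined protocol and SAP*

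**What the plan says.** Five places bear on this point.

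- **Section 6.1, Data Collection.** A laboratory abnormality enters the database as an AE only "if the laboratory abnormality is characterized by any of the following". The five criteria cover leaving the study because of it, accompanying symptoms or signs, a need for therapy ("Requires treatment or any other therapeutic intervention"), a link to a death or other SAE, and the investigator's judgement that the clinical impact is significant. A sixth bullet tells the investigator what to report about a clinically significant result; it is not a further criterion.
- **Section 6.1.2, Case Report Forms.** The adverse events to be recorded include "Grade 3 and 4 events that are possibly, probably or definitely related to the study drugs", with no laboratory exception, and all grade 5 events whatever their cause. Section 7.2.2 asks for the same classes at continuing review.
- **Section 3.3.1, Table 5 footnote 2 (sunitinib).** "Patients who develop Grade 3 or 4 lymphopenia may continue study treatment without interruption". At the investigator's discretion the same holds for grade 4 hyperuricemia and grade 3 hypophosphatemia without symptoms.
- **Section 8.** Safety is summarised as each patient's worst grade of each toxicity, by arm. "Should any particular type of toxicity result in 5 or more patients with grade 3-4 toxicity", the arms may be compared with a Cochran-Armitage trend test. The data source for the grades is not named.
- **Section 1.1.2.** Laboratory evaluations are among the safety endpoints listed as a secondary objective.

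**The concern.** Severity by CTCAE grade is what Section 8 tabulates and what 6.1.2 and 7.2.2 ask for, yet 6.1 admits laboratory values on other grounds. Section 6.1.2 selects among adverse events, so a value that never becomes an AE under 6.1 never reaches the form. The protocol does not say which rule governs.

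Two things are at stake. The by-arm table of severe toxicity may be too low for laboratory events. The shortfall may also differ between arms, because the two drugs have different rules for acting on the same laboratory finding.

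The grade 5 point is separate. The trigger follows a worst-grade tabulation and names grades 3-4, so read literally a fatal case does not count towards the five patients needed.

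**Working it through.** The plan gives no derivation, error rate or power for the five-patient trigger, so there is no stated figure to reproduce. The check is mainly of the text, followed by an illustration.

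**1. Grade 3-4 lymphopenia on sunitinib, no symptoms, treatment continued.** No discontinuation, no symptom, no treatment, no SAE. Four of the five routes are closed, and recording rests on investigator judgement. Asymptomatic grade 4 hyperuricemia and grade 3 hypophosphatemia follow the same path when treatment continues. Sections 6.1.2 and 7.2.2 would want all three if related.

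**2. Toxicity managed only by a dose hold.** Table 5 (sunitinib) and Table 9 (everolimus) call for a hold for Grade 3-4 neutropenia, among others. Section 6.1 does not say whether a hold is a therapeutic intervention. If it is, these events are recorded; if not, they fall back on investigator judgement.

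**3. Difference between arms.** If a hold does count, Table 8 interrupts everolimus for Grade 3 AEs (with metabolic exceptions) and for other Grade 4 events, while the sunitinib footnote permits continuing with hypophosphatemia or hyperuricemia. The same value could then be recorded in Arm 2 and not in Arm 1.

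**4. What incomplete recording does to the trigger (illustration only).** Inputs: 44 patients per arm and 88 in total (Section 8); sunitinib treatment-related rates for Grades 3-5 of 13.5% for neutropenia and 8.6% for thrombocytopenia (Section 11.1.2); an assumed share f of events that pass the 6.1 list. With q = rate × f,

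P(X ≥ 5) = 1 − Σ(k = 0 to 4) C(n,k) q^k (1 − q)^(n−k).

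Expected patients in one arm with f = 1: 44 × 0.135 = 5.9 and 44 × 0.086 = 3.8.

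| Toxicity | n | f = 1 | f = 0.75 | f = 0.5 | f = 0.25 |
|---|---|---|---|---|---|
| Neutropenia | 44 | 0.73 | 0.46 | 0.17 | 0.02 |
| Neutropenia | 88 | 0.995 | 0.95 | 0.72 | 0.18 |
| Thrombocytopenia | 44 | 0.33 | 0.15 | 0.04 | 0.002 |
| Thrombocytopenia | 88 | 0.88 | 0.68 | 0.33 | 0.04 |

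The n = 88 rows assume the sunitinib rates in both arms. Section 8 does not say whether the five patients are counted per arm or overall, so both are shown. The thrombocytopenia inputs agree with each other (6.8% + 1.8% = 8.6%). Those for neutropenia do not: Section 11.1.2 gives 0.3% for Grade 3 and 3.2% for Grade 4, which sum to 3.5%, not 13.5%.

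**5. Grade 5.** Section 11.1.2 gives 1.6% treatment-related grade 5 over all event types: 44 × 0.016 = 0.7, 88 × 0.016 = 1.4, and 120 × 0.016 = 1.9 at the accrual ceiling. Four Grade 3-4 cases plus two fatal cases of one toxicity would count as four and miss the trigger. If a toxicity has an 8.6% Grade 3-4 rate and an added grade 5 rate of 0.1%, counting grade 5 raises P(X ≥ 5) in 44 patients by 0.009. In the extreme case where all 1.6% falls on that one toxicity, the rise is 0.14.

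**The case against.** The strongest reply is that little need be lost. The investigator-judgement route can admit any asymptomatic Grade 3-4 value. Section 6.1.2 contains no laboratory exception, so a careful site may record all related Grade 3-4 values anyway. Section 8 does not say that it counts from AE records, and blood counts and chemistries are collected every cycle. Nothing here touches the primary endpoint, the sample size or a stopping rule.

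Much of that stands, and it limits what may be inferred:

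- A reader might infer that every asymptomatic Grade 3-4 value is lost. The fifth criterion prevents this: loss is possible and depends on the investigator.
- A reader might infer that the commonest severe laboratory toxicities of both drugs are understated. For hyperglycemia, Section 4.1.2.8 calls for medical therapy, which meets the treatment criterion. For neutropenia, thrombocytopenia and anemia it turns on the undefined status of a hold.
- A reader might take the drop from 0.73 to 0.17 as the size of the defect. It rests on an assumed share, one arm, and toxicities that are not the clear losses. No rates are given for those that are.
- A reader might infer that fatal toxicity disappears from the safety report. Grade 5 events are recorded whatever their cause, and the worst-grade table has no upper limit.

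The reply does not remove the inconsistency. An investigator who follows 6.1 as written may omit a related Grade 4 value that 6.1.2 and 7.2.2 call for. Section 6.4 ties CTCAE grading to AE reporting, and no section provides for grading raw laboratory values, so AE records are the likely, though unstated, source for Section 8.

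**Conclusion.** The concern holds in a limited form. The 6.1 list can exclude related Grade 3-4 laboratory toxicities that are asymptomatic and untreated, in conflict with 6.1.2 and 7.2.2. Lymphopenia, hyperuricemia and hypophosphatemia on sunitinib are the clear cases; toxicities managed only by a hold are uncertain. The consequence for the by-arm table depends on Section 8 using AE records, which is an inference. Its size cannot be stated, because the documents give no recorded share; the table above shows only that the trigger is sensitive to that share.

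The omission of grade 5 from the trigger is certain as a matter of wording and minor in effect: about 0.7 patients in 44 over all event types, affecting only a test that may or may not be run.

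This should be corrected because severe toxicity by arm is the main output for a stated secondary objective and the correction is cheap. It does not threaten the trial's main conclusion.

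**What to change.** 1. **Section 6.1:** add *is CTCAE Grade 3 or higher* to the list of criteria, so that it agrees with 6.1.2 and 7.2.2. This also makes the status of a dose hold irrelevant for Grade 3-4 values.
2. **Section 8:** state that laboratory toxicities in the table are graded by CTCAE directly from the scheduled CBC and listed chemistry values. Phosphate and uric acid are not in the scheduled panel (Section 3.4, note 2), so those two rely on the 6.1 edit. The calendar's treatment cycles list a CBC without mentioning a differential, as Section 2.2 does; confirm that one is reported, since lymphocyte and neutrophil grading needs it.
3. **Section 8 trigger:** change to *5 or more patients with grade 3 or higher toxicity*.

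No treatment rule changes. The cost is one line in 6.1, a sentence and a few words in Section 8, and programming on data already scheduled for collection. The downside is more laboratory AE entries and a less favourable toxicity table.
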